#### **Consolidation treatment: MidoHiDAC**

Each consolidation cycle is four weeks in duration, and should begin within two weeks following hematologic recovery (ANC  $\geq$  1000/µL and platelet count  $\geq$  50.000/µL), but not sooner than four weeks from the beginning of the previous cycle. If a consolidation cycle is delayed >8 weeks from

the start of the previous course of induction or consolidation due to slow resolution of toxicity or slow recovery of complete blood counts (CBC), please contact the SAL central study office.

### **MidoHiDAC**

Cytarabine	3000 mg/m  IV over 3 hrs twice daily	days 1,3,5
Midostaurin	50 mg (2 capsules) p.o. twice daily	days 8-21

High-dose cytarabine (HiDAC) 3000 mg/m^2 will be given by intravenous infusion over 3 hours every 12 hours on days 1, 3, and 5. Serial neurologic evaluation will be performed before and following the infusion of high-dose cytarabine.

It is recommended to administer dexamethasone 0.1% or other corticosteroid ophthalmic solution 2 drops to each eye four times per day to begin 6-12 hours prior to the initiation of the cytarabine infusion and to continue for at least 24 hours after the last cytarbine dose.

Midostaurin 50 mg (two 25 mg capsules) is given twice a day by mouth on days 8-21. Midostaurin is not given from day 22 of the current cycle and day 7 of the next consolidation cycle. Patients should take their doses at approximately the same time each day, and approximately 12 hours should elapse between the morning and evening doses. Each daily dose should be given with food and a glass of water (approx. 240 ml). Patients should be instructed to swallow capsules whole and not chew capsules. If vomiting occurs, no re-dosing is allowed before the next scheduled dose.

For **remission assessment**, a bone marrow aspirate (or bone marrow biopsy) must be performed one week after recovery of ANC  $\geq$  1000/µL and platelets  $\geq$  100,000/µL to document a complete remission. Remission assessment must be performed latest 35 days after the beginning of each consolidation cycle, even if ANC or platelets are below the described threshold.

If remission assessment shows < 5% myeloid blasts, the patient has a sustained CR/CRi and will continue treatment according to this protocol.

If remission assessment reveals  $\geq$  5% myeloid blasts, the patient has a relapse from CR/CRi and will discontinue study treatment. Patients who discontinue study treatment will be followed up until 25 months after study entry.

At each bone marrow aspiration, material should be obtained and sent to the central SAL laboratory in Dresden for MRD diagnostics (see section 7.4).

Three cycles of MidoHiDAC shall be administered depending on adequate blood counts and sufficient organ function.

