For **remission assessment**, a bone marrow aspirate (or bone marrow biopsy) must be performed every three months during maintenance treatment and during follow up including the end-of-study visit 9 months after the end of the 12-month-maintenance period or 25 months after study entry in case of premature discontinuation of study treatment. At each bone marrow aspiration, material should be obtained and sent to the central SAL laboratory in Dresden for MRD diagnostics (see section 7.4).

A suspected relapse during the entire study duration must be confirmed by bone marrow aspiration or biopsy.

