## 9 Endpoints for the Assessment of Efficacy and Safety

### 9.1 Efficacy

As pointed out in section 2.1, the reduction of overall survival in patients with c-KITmut is mainly due to a higher incidence of relapses while in FLT3-ITD patients, primary resistant disease leads to the inferior prognosis during the early course of the disease. Since the patient group in this trial consists both of c-KITmut and FLT3-ITD patients, event-free survival seems to be the measure to capture both early treatment failure in FLT3-ITD and later relapse from CR in c-KITmut patients. Therefore, the primary study endpoint will be the event-free-survival (EFS) rate at 2 years. Event-free survival will be defined as the time from inclusion in the study (date of signed informed consent) until either failure to achieve a CR/CRi five weeks after the beginning of the second induction therapy course), or hematological relapse from CR/CRi, or death from any cause. Revised IWG criteria will be used [17].

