#### 9.1.3 Relapse

### Any of the following, occurring after either CR or (CRi):

- The reappearance of circulating blast cells on more than one determination
- >5% AML blasts in the bone marrow, not attributable no another cause (e.g. bone marrow regeneration). If there are no circulating blasts, but the marrow contains 5%-20% blasts, a repeat marrow ≥ 1 week later with >5% blasts is necessary to meet the criteria for relapse.
- Development of extramedullary leukemia

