## 13.2 Target Variable/Endpoints

## 13.2.1 Primary Target Variable

As pointed out in section 2.1, the reduction of overall survival in patients with c-KITmut is mainly due to a higher incidence of relapses while in FLT3-ITD patients, primary resistant disease leads to the inferior prognosis during the early course of the disease. Since the patient group in this trial consists both of c-KITmut and FLT3-ITD patients, event-free survival seems to be the measure to capture both early treatment failure in FLT3-ITD and later relapse from CR in c-KITmut patients. Therefore, the primary study endpoint will be event-free survival (EFS).

Event-free survival rate at 2 years is defined as the time from study inclusion (date of informed consent) until either primary treatment failure or hematologic relapse or death from any cause occurs. Primary treatment failure is defined as the absence of CR/CRi five weeks (35 days) after the start of MidoDA induction treatment.

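### Haematological relapse, a component of primary EFS, is classified by two rules that disagree in a limited zone (5-20% marrow blasts without circulating blasts, exactly 5%, and regeneration), and no text says which rule governs the endpoint

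*Protocol*

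**What the plan says.** Section 7.1, under MidoHiDAC, sets the consolidation rule. If the remission marrow shows at least "5% myeloid blasts, the patient has a relapse from CR/CRi and will discontinue study treatment". It asks for no repeat, sets no condition on circulating blasts and makes no exception for regeneration. The same section fixes the timing: "Remission assessment must be performed latest 35 days after the beginning of each consolidation cycle, even if ANC or platelets are below the described threshold".

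Section 9.1.3 defines relapse after CR or CRi. Its marrow criterion is ">5% AML blasts in the bone marrow, not attributable no another cause (e.g. bone marrow regeneration"). For a marrow in the 5-20% range in a patient whose blood is free of blasts, it adds a further condition: "a repeat marrow ≥ 1 week later with >5% blasts is necessary to meet the criteria for relapse". Recurrent circulating blasts and extramedullary leukaemia are separate criteria and need no repeat marrow.

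Section 13.2.1 runs EFS from consent "until either primary treatment failure or hematologic relapse or death from any cause occurs". Section 9.1 gives the same components and adds "Revised IWG criteria will be used". Section 13.2.2 builds relapse-free survival and time to relapse on the same event, and the synopsis adds cumulative incidence of relapse. Under midostaurin maintenance, section 7.1 also says: "A suspected relapse during the entire study duration must be confirmed by bone marrow aspiration or biopsy".

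**The concern.** The same patient can be a primary-endpoint failure under one section and event-free under the other. The case at issue is a consolidation marrow with, say, 8% blasts, no circulating blasts, and a normal marrow a week or more later. Section 7.1 calls this a relapse from remission; section 9.1.3 does not. It can plausibly occur because a marrow is due by day 35 of each of three consolidation cycles even if counts have not recovered. That is when regeneration, the alternative explanation that section 9.1.3 itself names, could account for the blasts.

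Section 7.1 also ends study treatment on the first marrow and does not itself call for the repeat. A site that follows only 7.1 may never collect the result that 9.1.3 needs, and an analysis plan written later cannot supply it. With 18 patients and a fixed cut, the classification of a single patient can matter.

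**Working it through.** **1. The two rules side by side, for a consolidation marrow**

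| Finding | Section 7.1 | Section 9.1.3 | Agree? |
|---|---|---|---|
| More than 20% leukaemic blasts | relapse | relapse | yes |
| Above 5% and up to 20% AML blasts, circulating blasts present | relapse | relapse, no repeat needed | yes |
| 5-20%, no circulating blasts, repeat marrow not above 5% | relapse | not relapse | **no** |
| 5-20%, no circulating blasts, repeat marrow above 5% | relapse at first marrow | relapse, date not stated | event yes, date open |
| Exactly 5% | relapse (at least 5%) | below the main threshold (more than 5%), yet inside the 5-20% repeat zone | **no** |
| Above 5%, attributed to regeneration | relapse (myeloid blasts, no exception) | not relapse | **no** |

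**2. The plan's own design figure**

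Inputs from section 13.3: n = 18, cut 13, p0 = 0.5, p1 = 0.8, one-sided 5%, power 80%.

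- Exact alpha: P(X ≥ 13 | 18, 0.5) = (8568 + 3060 + 816 + 153 + 18 + 1) / 2^18 = 12616 / 262144 = 0.048.
- Exact power: P(X ≥ 13 | 18, 0.8) = 0.867.
- 18 is the smallest n with alpha at most 0.05 and power at least 0.80. The stated design is therefore correct; 80% is a minimum, not an error.

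**3. One patient at the cut**

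- 13/18: p = 0.048; one-sided 95% exact lower bound 0.502, which excludes 0.5.
- 12/18: p = 31180 / 262144 = 0.119; lower bound 0.446, which does not exclude 0.5.

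Under section 13.5 the treatment is declared effective in the first case and not in the second.

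**4. Illustration of the effect on power**

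The documents give no rate of transient 5-20% marrows. Let q be an assumed rate per marrow. Assume three independent marrows per patient, and that every affected patient would otherwise be event-free at two years.

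Fraction affected: f = 1 − (1 − q)^3. Apparent success rate: 0.8 × (1 − f). Power: P(X ≥ 13) at that rate.

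| q | f | Apparent rate | Power |
|---|---|---|---|
| 0 | 0 | 0.800 | 0.867 |
| 0.5% | 1.5% | 0.788 | 0.836 |
| 1% | 3.0% | 0.776 | 0.802 |
| 2% | 5.9% | 0.753 | 0.728 |
| 3% | 8.7% | 0.730 | 0.647 |

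**5. Direction of the error**

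The same reduction applied at p0 = 0.5 lowers the rejection probability. At f = 5% the rate is 0.475 and P(X ≥ 13) = 0.030, against 0.048.

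**The case against.** The best answer is that the endpoint definition already has a home. Section 9 is the endpoints chapter, 9.1.3 carries the title Relapse, and section 9.1 invokes the revised IWG criteria. Section 7 is the treatment plan, so its sentence can be read as telling sites when to stop treatment. Section 6.3 makes a primary event a reason to stop, but it also lists reasons to stop that are not events, so stopping under 7.1 does not in itself create an EFS event.

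Much of this stands, and it lowers the weight of the point. It does not remove the contradiction. Section 7.1 does not merely stop treatment: it says that the patient has relapsed from CR/CRi, which is the event that sections 6.3 and 9.1 name. No sentence limits 7.1 to treatment or gives 9.1.3 precedence. The requirement to confirm a suspected relapse by marrow, and the relapse column and footnote in the visit schedule, do not say whether one marrow is enough.

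Stronger readings are tempting but are not supported:

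- **Section 9.1.3 requires a repeat marrow for every relapse.** It does so only for 5-20% without circulating blasts.
- **The conflict could produce a false positive result.** The single-marrow rule only adds events, so it is conservative against p0.
- **There is a known, material loss of power.** No document gives the rate. In the illustration, power stays above 80% up to about 1% per marrow, and a patient who later relapses or dies within two years is an event under either rule.
- **The one-patient sensitivity measures this defect.** Any 13-of-18 rule has it; it shows only why the classification must be unambiguous.
- **The rule will be chosen after the results are seen.** The text leaves room for that, but nothing suggests that it is intended.

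**Conclusion.** The point holds as a contradiction between two stated rules for one component of the primary endpoint. It is confined to three situations: 5-20% marrow blasts without circulating blasts, exactly 5%, and blasts attributable to regeneration. It carries over to relapse-free survival, time to relapse and cumulative incidence of relapse.

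If such a patient sits at the cut, the trial's conclusion changes. The general effect is lower EFS and lower power, with no inflation of type I error. How much power is lost cannot be known from the documents; the range 0.836 to 0.647 rests wholly on the assumed rates, on independence, and on affected patients otherwise being successes. Section 9.1.3 is the natural definition for the endpoint, and what is missing is a statement that it governs. The grade is therefore should-fix, not a defect that invalidates the design.

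**What to change.** 1. In sections 9.1 and 13.2.1, state that the relapse event for EFS, relapse-free survival, time to relapse and cumulative incidence of relapse is determined by the section 9.1.3 criteria only.
2. Make the boundary at exactly 5% consistent, both between the sections and within 9.1.3.
3. State which date counts as the date of relapse when a repeat marrow is used.
4. Reconcile the sentence in section 7.1 that classifies relapse and stops treatment with section 9.1.3. Which treatment rule is right is for the trial's clinicians, and no view is taken here.

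The cost is a few sentences in the protocol. Section 9.1.3 already requires the repeat marrow, so no new procedure is added, and n = 18 and the cut of 13 do not change.

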### Midostaurin maintenance

Patients who continue in complete remission (by bone marrow aspiration and blood evaluation) after three cycles of consolidation therapy will receive midostaurin maintenance therapy. If, in the opinion of the investigator, the clinical condition of a patient does not allow a third cycle of MidoHiDAC, the SAL central study office should be contacted for medical advise. If the LKP agrees that the risk of serious adverse events is too high in case of a third MidoHiDAC application, midostaurin maintenance may commence after two cycles of MidoHiDAC.

Prior to initiation of midostaurin maintenance therapy, all significant acute toxicity from consolidation therapy must have resolved to grade 2. Maintenance will begin after hematologic recovery (ANC  $\geq$  1000/ µL, platelet count  $\geq$ 50,000/µL) from remission consolidation and no sooner than 14 days after the last midostaurin application in the last cycle of MidoHiDAC, i.e. earliest on day 36 after the beginning of the last cycle of MidoHiDAC. Maintenance treatment must be started before day 64 after the beginning of the last cycle of MidoHiDAC, i.e. patients who cannot start maintenance treatment until 64 days after the beginning of the last cycle of MidoHiDAC, i.e. patients who cannot start maintenance treatment until 64 days after the beginning of the last cycle of MidoHiDAC, i.e. patients who cannot start maintenance treatment until 64 days after the beginning of the last cycle of the last cycle of MidoHiDAC will stop study treatment and will be followed up until 25 months after study entry.

Maintenance treatment consists of continuous midostaurin application for 12 cycles with 28 days per cycle:

Midostaurin50 mg (2 capsules) p.o. twice dailydays 1-28Start of new maintenance cycle on day 29

Midostaurin 50 mg (two 25 mg capsules) is given twice a day by mouth on days 1-28. Patients should take their doses at approximately the same time each day, and approximately 12 hours should elapse between the morning and evening doses. Each daily dose should be given with food and a glass of water (approx. 240 ml). Patients should be instructed to swallow capsules whole and not chew capsules. If vomiting occurs, no re-dosing is allowed before the next scheduled dose.

For **remission assessment**, a bone marrow aspirate (or bone marrow biopsy) must be performed every three months during maintenance treatment and during follow up including the end-of-study visit 9 months after the end of the 12-month-maintenance period or 25 months after study entry in case of premature discontinuation of study treatment. At each bone marrow aspiration, material should be obtained and sent to the central SAL laboratory in Dresden for MRD diagnostics (see section 7.4).

A suspected relapse during the entire study duration must be confirmed by bone marrow aspiration or biopsy.

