	survival (OS), Relapse-free survival	(RFS), morphologic and molecular				
	CR rate, incidence of AEs/SAEs, MR	D kinetics				
TIMETABLE	Enrolment of first subject (FPFV)*:	1 May 2012				
	Enrolment of last subject:	30 April 2016				
	End of trial for last subject (LPLV)*:	31 May 2018				
	Closing of database	31 July 2018				
	Conclusion of statistical evaluation:	1 August 2018				
	Integrated final report:	30 September 2018				
	Treatment duration per subject: 16 months					
	Estimated duration of follow-up 9 months					
	Study duration per subject 25 months					
	Planned interim analysis: none					
	*Study begin/end is generally the first/last visit of the first/last subject					
SAMPLE SIZE	n = 18 patients					
	midostaurin 50 mg (two 25 mg capsu	ules) is given in combination with the				
	second of two induction cycles and	in combination with three cycles of				
	gh-dose cytarabine (HiDAC) consolidation chemotherapies and					
	maintenance treatment in patients w	vith c-kit or FLT3-ITD positive t(8;21)				
	part of the study	gn. The first cycle of induction is not				
	Second cycle of induction chemotherapy (7+3 scheme).					
	Cytarabine 100 mg/m  days 1-7					
	Daunorubicin 60 mg/m  days 3-5					
	Midostaurin 50 mg (2 capsules) twice	e daily days 8-21				
	Triple consolidation chemotherapy:					
	Cytarabine 3000 mg/m  twice daily d	ays 1, 3, 5				
	Midostaurin 50 mg (2 capsules) twice daily days 8-21					

	Maintenance treatment:				
	Midostaurin 50 mg (2 capsules) twice daily continuously for 12 months				
Main Inclusion Criteria	
 
Diagnosis of c-KIT mutated t(8;21) AML i.e.
 
>20% myeloid blasts in bone marrow and/or peripheral blood at initial diagnosis
 
Plus cytogenetic diagnosis of aberration t(8;21)/AML1-ETO
 
Plus mutation of c-KIT gene (mut-KIT17 or mut-KIT8) or FLT3-ITD mutation or both c-KIT and FLT3-ITD mutations
 
Chemoresponsive disease as determined by early bone marrow assessment on day 14-16 after first cycle of induction therapy with cytarabine in combination with daunorubicine or idarubicine, or mitoxantrone
 
Fit for further intensive chemotherapy
 
Age 18-65 years
 
ECOG performance status of 0-2
 
Life expectancy of at least 12 weeks
 
[Exact list of inclusion criteria is specified in section 5.3]
 
				

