### 7.4 Study Evaluations

	Screening examination within 7 days before study entry	Day 1of 2 nd induction and Day 1 of each consolidation	Day 1-28 of 2 nd induction and each consolidation	Remission control†	Start maintenance	During maintenance	Within 14 days after end of maintenance	Follow-up 3, 6+9 months after end of maintenance	Relapse
Screening Examination	х								
Check In- and Exclusion Criteria	х								
Registration	х								
Toxicity Assessment (AE)			х		х				
Toxicity Assessment (SAE)			х		х	Monthly	Х	х	
Physical Examination incl. blood pressure, pulse and weight	х	x			x	monthly	х	х	
CBC (incl. differential and plts)	х	x	2x/week	х	x	monthly	х	х	х
Chemistry and Coagulation: Na, K, Ca, Crea, Mg, Urea, ALAT, ASAT, AP, Bili, Total Protein, Albumin, Uric Acid, Glucose, INR, PTT, Fib	х	x	2x/week		x	monthly	x	х	х
fT4, TSH	х								
Urinalysis	х								
Bone marrow cytology	х			х		Q 3 months *		х	х
Bone marrow cytogenetics	х			х		Q 3 months *		х	Х
Bone marrow molecular genetics	х			х		Q 3 months *		х	х
EKG (QTc Interval)	х	Х	**		**	**			
Chest X-Ray (pa and lateral)	х								
Echocardiography (LVEF)	х								
Beta-HCG pregnancy test	х								
Concomitant Medication			Х			х			

† latest day 35 after beginning of each course of chemotherapy

\* and in case of suspected or overt relapse for confirmation

\*\* days 1,3,14 of midostaurin during induction 2 and each cycle of consolidation (days 8,10,21 of induction 2 and consolidation) and monthly during maintenance

Molecular and cytogenetic analyses will be done in the central SAL reference laboratory. With each bone marrow aspiration, material for central MRD diagnostics should be obtained and sent to the following address:

Universitätsklinikum Carl Gustav Carus, Medizinische Klinik und Poliklinik I, Hämatologisches Labor [name], [contact], [contact].

For information on results, please contact [name]. [name], [contact].

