## **13.3 Sample Size Calculation**

The primary endpoint is a binary variable indicating event-free-survival at 2 years. The reference 2year-EFS rate was obtained from data of the SAL study group including 104 patients with t(8;21). Of the 104 patients, 78 did neither display FLT3-ITD nor c-KITmut. Eight patients were FLT3-ITD positive and 18 patients displayed a c-KIT mutation.

Reference 2-year-EFS rate of a historical cohort: p0 = 0.5Success rate of interest: p1 = 0.8Difference between reference and success rate of interest:  $\delta = 0.3$ nullhypothesis:  $p \le p0$ alternate hypothesis:  $p \ge p1$ power: 80% significance level: 5% one sided The nullhypothesis of this trial is that the 2-year-EFS rate is worse or equal to 0.5 under the experimental treatment. The alternate hypothesis is that the 2-year-EFS-rate is equal to 0.8 or greater. In an exact single stage phase 2 design 18 patients have to be enrolled to be able to detect the critical difference in the EFS-rates of 0.3 with a power of 80% and a one-sided significance level of 5%. The nullyhpothesis can be rejected if after 2 years 13 or more of 18 patients are without an event. The calculation is based on the exact binomial distribution as described in A'Hern [27].

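### The primary endpoint is event-free status at 24 months from consent, but no remission assessment is tied to month 24, and the fastest completers can end follow-up before it

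*Protocol*

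**What the plan says.** Section 13.3 states: "The primary endpoint is a binary variable indicating event-free-survival at 2 years". Section 13.2.1 sets the clock: "Event-free survival rate at 2 years is defined as the time from study inclusion (date of informed consent) until either primary treatment failure", hematologic relapse or death. The decision rule in 13.3 is "The nullyhpothesis can be rejected if after 2 years 13 or more of 18 patients are without an event", with "power: 80% significance level: 5% one sided".

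Surveillance is fixed in 7.1 (Midostaurin maintenance) and in the table of 7.4. Marrow is done every three months during maintenance and follow-up, "including the end-of-study visit 9 months after the end of the 12-month-maintenance period or 25 months after study entry", the latter for patients who stop treatment early. The table heads the follow-up column "Follow-up 3, 6+9 months after end of maintenance", and blood counts in follow-up sit in that same column. The Synopsis gives 16 months of treatment, 9 months of follow-up and "Study duration per subject 25 months".

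For completers, follow-up is 9 months from the end of maintenance (4.3 and 7.1), not a fixed time from study entry. Section 13.4 excludes patients whose 2-year status cannot be evaluated from the primary analysis and adds worst-case and best-case analyses.

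**The concern.** The time point that decides the trial and the visits that supply the data run on different clocks. Two gaps follow.

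1. **Reading before the next look.** On the nominal plan no marrow or blood count is scheduled between about months 22 and 25. A relapse that arises silently in months 22 to 24 is first seen at the later marrow. If it is dated when found, the patient is event-free at 2 years.
2. **Follow-up that ends too soon.** A completer who moves quickly through the cycles can have the last visit before month 24. Such a patient may have no evaluable 2-year status and leave the primary analysis under 13.4.

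The rule has little room for either. One patient separates 12 from 13 of 18, and the exact error rate is already close to 5%. The visit anchor is set only in the protocol; an analysis plan cannot create an assessment that was never scheduled.

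**Working it through.** **The plan's own figure.** With X ~ Binomial(18, p), P(X ≥ 13) is 0.0481 at p = 0.5 and 0.867 at p = 0.8. The smallest n with one-sided error at most 5% and power at least 80% is 18, with 13 as the cut-off, so 13.3 reproduces. The one-sided 95% lower limit (13.5) is 0.502 for 13/18 and 0.446 for 12/18.

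**When the last two marrows fall.** Inputs: at least four weeks between cycle starts (7.1, consolidation); maintenance earliest on day 36 of the last consolidation cycle, taken as 35 days elapsed; 12 × 28 = 336 days of maintenance (4.3); visits 6 and 9 months later. One month is 30.4375 days.

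| Path | Days to end of maintenance | +6 months | +9 months |
|---|---|---|---|
| Nominal (Synopsis) | 16 months | 22 | 25 |
| Shortest, three consolidations | 28+28+28+35+336 = 455 (14.95 months) | 20.95 | 23.95 |
| Shortest, two consolidations (allowed in 7.1) | 28+28+35+336 = 427 (14.03 months) | 20.03 | 23.03 |
| 35-day cycles, maintenance after 42 days, 7 days from consent | 7+35+35+35+42+336 = 490 (16.10 months) | 22.10 | 25.10 |
| 8-week cycles, maintenance after 63 days, 7 days from consent | 7+56+56+56+63+336 = 574 (18.86 months) | 24.86 | 27.86 |

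The two shortest paths assume induction starts on the day of consent. Seven days between consent and induction move their last visits to 24.18 and 23.26 months.

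**Possible effect of the 22-to-24-month gap.** Assumptions: constant hazard, true 2-year rate p, last look at month 22, and a fraction f of the events in months 22 to 24 first seen at the later marrow and dated then. Apparent rate: q = p + f × (p^(22/24) − p).

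At p = 0.5, 0.5^(22/24) = 0.5297, so at most 3.0 points, or 18 × 0.0297 = 0.54 patients, are affected.

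| f | q | P(X ≥ 13) |
|---|---|---|
| 0 | 0.500 | 4.8% |
| 0.25 | 0.507 | 5.5% |
| 0.5 | 0.515 | 6.2% |
| 1 | 0.530 | 7.9% |

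At p = 0.8, f = 1 gives q = 0.815 (0.27 patients) and power 0.901 instead of 0.867.

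**Sensitivity to the hazard shape.** Front-loaded Weibull hazards through 0.5 at month 24 give 6.9% (shape 0.7) and 6.2% (shape 0.5) at f = 1. Shape 0.5 with f = 0.5 gives 5.5%, and with f = 0.25, 5.1%.

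**What the fix can cost.** If every patient were read at month 25 and all events up to then counted, the rates under constant hazard would be 0.5^(25/24) = 0.486 and 0.8^(25/24) = 0.793. Type I error would be 3.7% and power 0.848, still above the planned 80%. A +4-week window ends at 24 + 28/30.4375 = 24.92 months, so the cost is no larger than about this.

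**The case against.** A reader might infer that the protocol makes a relapse found at month 25 a 2-year success and so inflates the success count. The document does not say that. Sections 9.1 and 13.2.1 run the time until relapse and give no dating rule. Such a rule is commonly left to the analysis plan, and the patient could equally be scored as an event or as not evaluable.

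A reader might also take 7.9% as the trial's true error rate. It is only an upper bound. It defers every event in months 22 to 24, including deaths, which are dated exactly; if 20% of them were deaths without relapse (an assumption), the figure is 7.2%. It also ignores relapses found between visits. Section 9.1.3 counts circulating blasts and extramedullary disease, and 7.1 requires a marrow whenever relapse is suspected. In follow-up, though, no blood count is scheduled between visits, so such detection rests on symptoms or on care outside the schedule.

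The strongest objection concerns the comparator. The reference rate of 0.5 is itself observed, in a historical cohort whose assessment schedule is not given. Similar gaps there would cancel some or all of the shift, and wider gaps would make the trial's schedule work against midostaurin. The net direction against the reference is therefore unknown.

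These points limit the size. They do not supply a 24-month assessment, and they do not help completers whose last visit comes before month 24.

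**Conclusion.** The point holds as a design gap of modest size. No remission assessment is anchored to the time at which the primary endpoint is read. Nominal patients and early stoppers have their closing look about a month late, and the fastest completers can have it up to about one month early (23.0 to 24.0 months).

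If relapses are dated at detection and the hazard is constant, type I error at a true rate of 0.5 would be about 5.5-6.2% rather than 4.8% when a quarter to a half of the late events wait for the visit, and 7.9% at most. A front-loaded hazard makes it smaller. How many completers would finish before month 24 cannot be told from the protocol. The documents support an unfixed reading at the decision time point; they do not support a claim that the result will be biased in favour of midostaurin.

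**What to change.** In 7.1, 7.4 and 13.2.1:

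- Anchor the final already planned follow-up marrow and blood count to 24 months after study inclusion for every patient, completers and early stoppers (for example 0 to +4 weeks), and follow every patient at least to that visit. Where a slow course already puts the 6-month visit in that window, it can serve.
- State that 2-year status is read at this assessment and that a relapse found there counts as an event. The anchor alone is not enough, because a relapse found inside the window would still carry a date after month 24. The scoring sentence alone is not enough either, because it leaves the fastest completers without a reading.
- Give scoring by detection date as a sensitivity analysis.

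Cost: one moved visit and a few sentences, with no change to treatment or sample size. The few relapses that arise between month 24 and the visit count as failures, which lowers power slightly (0.848 at worst in the calculation above, against 0.867). The fastest completers are followed up to about one to two months longer (24.92 − 23.03 = 1.89 months at most).
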